6.5.1.5. Choice of chest physiotherapy treatment

The clinical physiotherapist will define the chest physiotherapy treatment modalities according to the formulated clinical hypothesis. The following treatments may be proposed :

- No chest physiotherapy treatment indicated;
- Refer to the intensivist;
- Non-invasive ventilation;
- CPAP (if non-ventilated patient) or PEEP modifications (if ventilated patient);
- Manual or ventilator hyperinflation;
- Mechanical in-exsufflator (Cough Assist ©);
- Rib cage compressions, manual assisted cough;
- Endo or naso-tracheal suctioning;
- Positioning;

- Semirecumbent position (head 45° from bed);
- Laterocubitus;
- Early mobilization:
 - Sitting on side of bed;
 - Standing;
 - Sitting on chair.

The choice of treatment according to the clinical hypothesis is defined in annexe 2b. The clinical physiotherapist will define the chest physiotherapy treatment modalities for the primary clinical hypothesis. The chest physiotherapy treatment modalities will be defined both before and again separately after the LUS and Diaphragm US examination.

6.5.2. Procedure 2: Lung and diaphragm US

6.5.2.1. *Ultrasound physiotherapist/operator*

The LUS will be performed by the physiotherapist/operator, who will be blinded to the clinical evaluation by clinical physiotherapist, the patient's status including the Chest X-rays and CT-scan findings and all of other clinical information. The operator will not take part in the management of the patients concerned.

The ultrasound training of the operator in the French ICU was performed as follows:

- Two days academic theoretical and practical training;
- One year supervised lung ultrasound practice: more than 200 supervised thoracic ultrasound examinations performed;
- Two years autonomous thoracic ultrasound practice.

The Australian ICU used a modified version of this training program with a one day theoretical and practical training course and supervised lung ultrasound practice.

6.5.2.2. *Ultrasound examination modalities*

A referent intensivist will be present when LUS is performed by a french physiotherapist, in order to control the adequate realization of LUS examination. Referent intensivists are trained to LUS. [name] [name] (Forcilles' Hospital), [name] [name] (St. Joseph's Hospital) and Pr [name] (University Hospital of Dijon) will be referent intensivists.

The CX 50 (Philips) or Edge (Sonosite) ultrasound machine, with 3.5 MHz convex and 10 MHz linear probes, will be used. The convex probe will be used to assess the lung (interstitial syndrome, consolidation, pneumothorax, diaphragm excursion and pleural effusion) and the linear probe will be used to assess to evaluate diaphragm thickness.

The patient will be in semirecumbent position (head 30° from bed) for LUS imaging. Two lines delimit the axillary space: the anterior and posterior axillary lines. These lines define

areas of investigation for each hemithorax—anterior, lateral, and posterior—each of which is divided into upper and lower parts. Each hemithorax includes 6 examination areas (*cf annexe 3a*). The locations of the liver and spleen allow for the identification of the right and left diaphragm cupolas, which separate the thoracic and abdominal compartment. The probe will be used to explore each intercostal space using a longitudinal view. Specific examination modalities for the diaphragm ultrasound are defined in annexe 3a.

6.5.2.3. *Lung and diaphragm ultrasound semiology*

The basics lung ultrasound semiology is described in annexe 3b. The following syndromes will be searched for: normal profile, alveolar-interstitial syndrome, pulmonary consolidation, pleural effusion, pneumothorax and diaphragm dysfunction (16).

The ultrasound syndromes are defined by the following signs in a scanned for the in six-lung zones of each chest wall of the patient:

Normal lung:

- Bat sign;
- A lines;
- Pleural sliding (seashore sign).

A normal profile is compatible with presence of tracheo-bronchial retained secretions and bronchospasm.

Alveolar-interstitial syndrome(16–18):

- A positive region is defined by the presence of three or more B-lines in a longitudinal plane between two ribs;
- In the anterior and lateral thoracic areas;
- Multiple and well-defined B-lines: moderate loss of lung aeration;
- Confluent B-lines: severe loss of lung aeration.

The presence of a focal sonographic pattern of interstitial syndrome is compatible with pneumonia, atelectasis or pulmonary contusion.

The presence of multiple diffuse bilateral B-lines is compatible with pulmonary oedema or ARDS. In the case of pulmonary oedema, the interstitial syndrome is diffuse, homogeneous and bilateral. In the case of ARDS, the interstitial syndrome is diffuse, heterogeneous, bilateral and associated with pleural abnormalities and sub-pleural consolidations.

Lung consolidation:

- Subpleural echo-poor region or tissue-like echo-structure;
- Atelectasis pattern(19,20):

- Abolished pleural sliding;
 - Static air bronchogram;
 - Lung pulse;
 - Passive atelectasis due to compression from the surrounding pleural effusion: homogeneous echogenic structure into the pleural effusion, with smooth margin and linear air bronchogram(21).
- Pneumonia pattern(22–25):
- Irregular deep margin when the consolidation is partial;
 - Regular deep margin when consolidation involves an entire lobe;
 - Static or dynamic air bronchogram;
 - Fluid bronchogram;
 - Vascular pattern;
 - Bilateral or unilateral.

The aim of physiotherapist is not to identify the medical diagnosis. Regarding the presence of the interstitial syndrome and lung consolidation, the aim is to also define the level of lung aeration present in each of the 12 lung zones:

- Normal aeration (N): presence of lung sliding with A-lines or fewer than two isolated B-lines;
- Moderate loss of lung aeration (B1): multiple, well-defined B-lines (B1 lines);
- Severe loss of lung aeration (B2): multiple, coalescent B-lines (B2-lines);
- Lung consolidation (C): presence of a tissue pattern.

Points will be allocated according to the worst ultrasound pattern observed: N=0, B1=1, B2=2, C=3. Sum of scores for each area defines the LUS score, ranging between 0 and 36(26).The qualitative description of the consolidation allows the physiotherapist to differentiate atelectasis or pneumonia pattern and the adaptation of the chest physiotherapy treatment (*cf annexe 2b*).

Pleural effusion (16):

- Anechoic or hypoechoic structure ;
- Quad sign ;
- Sinusoid sign ;
- Transudates are always anechoic, while exudates are echoic and loculated (18).

Pneumothorax (16) :

- Lung point;

- Absence of pleural sliding (stratospheric sign);
- Absence of B-lines;
- Absence of lung pulse.

Diaphragmdysfunction :

- Diaphragm excursion < 2,5 cm(27);
- Diaphragmthickening fraction < 20% (28).

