6.5.1.4. Clinical hypotheses

Following the examination, he/she will put forward one or several hypotheses concerning the respiratory dysfunction (and not the medical diagnosis) and will either confirm or refute the indications for chest physiotherapy (*cf. annexe 2a*). If chest physiotherapy is indicated, the physiotherapist will specify the protocol to be used. The choice of the treatment modalities with regard to the type of respiratory dysfunction is detailed in annexe 2b.

According to the clinical examination, the clinical physiotherapist formulates one or more of the following clinical hypothesis (*cf annexe 2a*):

- Clinical examination is compatible with retained airway secretions;
- Clinical examination is compatible with bronchospasm;

- Clinical examination is compatible with pneumonia/consolidation;
- Clinical examination is compatible with atelectasis (~~passive or obstructive~~active mechanism);
-
- Clinical examination is compatible with pleural effusion;
- Clinical examination is compatible with pulmonary edema or global interstitial syndrome;
- Clinical examination is compatible with pneumothorax;
- Clinical examination is compatible with reduced aeration at the most dependent parts of the lungs;
- Clinical examination is compatible with unilateral diaphragm dysfunction (~~unilateral or bilateral~~);
- Clinical examination is compatible with bilateral diaphragm dysfunction;
- Clinical examination is inconclusive.

Among the formulated clinical hypotheses, the clinical physiotherapist will choose one primary clinical hypothesis (the choice is left to the discretion of the clinical physiotherapist, based on the probability and priority of the clinical hypothesis in terms of treatment).

A lung and diaphragm US will be done (see below) following the evaluation of the clinical physiotherapist with the physiotherapist who undertakes the US assessment blinded to the clinical assessment findings of the clinical physiotherapist. The clinical physiotherapist will then incorporate the results of the lung and diaphragm US and deem whether they are compatible with the clinical hypotheses put forward. He/she will then specify the chest physiotherapy protocol according to the results of the US-scan.

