6.5.2.4. Lung and diaphragm ultrasound report

The physiotherapist/operator will write a detailed LUS-scan report, which will be given to the clinical physiotherapist. When LUS is performed by a french physiotherapist, the LUS report will be checked and validated by the referent intensiviste.-The LUS-scan report# will include the LUS and Diaphragm diagnosis and describe the signs observed in the different regions of the chest (*cf. annexe4*). The clinical physiotherapist is trained to interpret LUS reports. The clinical physiotherapist then determines the options or changes to treatment based on the US findings.

7. Studyprogress

7.1.Study planning

- Ethic comittee submission: December 2016;
- Study comencement: January 2016;
- Inclusion duration : 12 months;
- Length of patient participation: one day;
- End of inclusion: January 2017;
- Total duration of the study: 18 months;
- Congress communications: French Intensive Care Society Congress, ESICM, ERS, ATS, from April 2018;
- Publication: September 2018;
- Target journal: Physical therapy, Intensive Care Medicine or Critical Care Medicine.

7.2.Recruitment method

Patients will be recruited in the Surgical ICU of the CHU de Dijon, Medical-Surgical ICU of Paris St. Joseph's Hospital, Respiratory ICU and Post-ICU Rehabilitation Unit of Forcilles' Hopital and the ICU of St Vincent's Hospital.

Patients admitted to the ICU and who meet the inclusion criteria will be invited to take part in the study. Patients with hypoxemia will be identified by the duty physician at the time of

transfer to the unit or by the principal investigator and the coordinating investigator during the day. Written informed consent will be collected (*cf. annexes 5a and 5b*).

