PSL: Parasternal line; AAL: Anterior axillary line; PAL: Posterior axillary line

Scanning procedure

[figure not shown]
Interstitial syndrome: Investigation is performed at the anterior and lateral thoracic areas. A positive region is defined by the presence of three or more B-lines in a longitudinal plane between two ribs, and a positive exam suggests the presence of two or more positive regions. A convex probe is used.

Consolidation: Examination begins with the lung area of interest (refer to clinical assessment) and may involve the entire lung if necessary. A convex probe is used.

Pneumothorax: In the supine patient, the sonographic technique consists of exploration of the least gravitationally dependent areas progressing laterally. A convex or a linear probe may be used.

Pleural effusion: In the supine patient, the ultrasound probe is placed in the postero-inferior area in the transverse view. The maximum distance between the parietal and visceral pleura (PLD) is measured 3 cm above the inferior pole of the lung at the end of expiration.

Diaphragm assessment – excursion and thickness *(If ventilated patient use PSV mode with PS = 7 and PEEP = 0)*

Diaphragm excursion: Anterior subcostal approach: the probe is placed between the anterior axillary line and the mid-clavicular line. B-mode is initially used to determine the best approach and select the exploration line. After the diaphragm is identified, excursion measurements are performed in M-mode: the diaphragm moves toward the probe during inspiration and away from it during expiration. The distance between the end-inspiration and end-expiration points defines the diaphragm excursion. A diaphragm excursion < 2.5 cm (Lerolle Chest, 2009) indicates a diaphragm dysfunction.

Diaphragm thickening: the probe is placed in an intercostal space between the mid-axillary line and the anterior axillary line, 0.5 cm to 2 cm below the costo-diaphragmatic sinus. In B-mode, the diaphragm is observed as a structure made of three distinct layers: a non-echogenic central layer bordered by two echogenic layers. The diaphragm thickening fraction (DTF) measurement is obtained in B-mode using the following formula: $DTF (\%) = [(end-inspiration\ thickness - end-expiration\ thickness) / (end-expiration\ thickness) \times 100]$. A DTF < 25% indicates a diaphragm dysfunction.

Annexe 3b: LUS Semiology

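### Diaphragm dysfunction on ultrasound has two thickening-fraction cut-offs, below 20% in section 6.5.2.3 and below 25% in Annexe 3a, and no rule says which prevails

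*Combined protocol and SAP*

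**What the plan says.** Section 6.5.2.3 introduces its list with "The ultrasound syndromes are defined by the following signs". For the diaphragm it gives two signs: "Diaphragm excursion < 2,5 cm(27") and "Diaphragmthickening fraction < 20% (28"). It does not say whether one sign is enough or both are needed.

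Annexe 3a describes how each diaphragm measurement is made and closes each description with its own cut-off. For excursion it has "A diaphragm excursion < 2.5 cm", which agrees with section 6.5.2.3. For thickening fraction it has "A DTF < 25% indicates a diaphragm dysfunction", which does not.

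The main text points to the annexe once on this subject, in section 6.5.2.2: "Specific examination modalities for the diaphragm ultrasound are defined in annexe 3a". The report form in Annexe 4 has fields for thickness, thickening fraction and excursion on each side, and an entry for unilateral or bilateral diaphragm dysfunction. It prints no cut-off. For French operators, section 6.5.2.4 adds that "the LUS report will be checked and validated by the referent intensiviste".

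**The concern.** A diagnostic label that feeds the analysis needs one definition. Here an operator can follow section 6.5.2.3 or Annexe 3a, comply with the plan either way, and reach opposite labels on the same scan.

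The label reaches the analysis by four routes.

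- **Compatibility.** Under section 6.5.1.4 the clinical physiotherapist takes the ultrasound results and must "deem whether they are compatible with the clinical hypotheses put forward". Section 8.2.1 uses that judgement to split patients into events and non-events.
- **Treatment modification.** Annexe 2b has a separate treatment row for diaphragm dysfunction, so the label may also influence whether the physiotherapy plan is recorded as changed. That is the other axis of the NRI.
- **Subgroup NRIs.** Section 8.2.2 calculates an NRI for each clinical hypothesis, which includes unilateral and bilateral diaphragm dysfunction, and for each centre. If sites adopt different cut-offs, the difference could look like a centre effect.
- **Kappa.** Diaphragm dysfunction is category T7 in section 8.2.3.

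**Working it through.** The plan has no figure of its own to reproduce on this point. The check compares the two texts and then works out what the gap means.

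**1. Is the conflict real?**

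| | Section 6.5.2.3 | Annexe 3a |
|---|---|---|
| Excursion | < 2.5 cm | < 2.5 cm |
| Thickening fraction | < 20% | < 25% |

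Only the thickening fraction differs. The two values are not assigned to different patients, sides, ventilation modes or grades of severity, and neither stands in an amendment log.

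**2. Does any text settle it?** The opening of section 6.5.2.3 is definitional and favours 20%. The cross-reference in section 6.5.2.2 concerns how the examination is done, but it takes the operator to the page where 25% stands beside the formula. Annexe 4 is silent. The referent intensivist who validates French reports is not told which value to apply.

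**3. Which scans change label?** Annexe 3a gives DTF (%) = (Ti − Te) / Te × 100, with Ti and Te the end-inspiratory and end-expiratory thickness. The disputed band is 20% ≤ DTF < 25%, that is 1.20 ≤ Ti/Te < 1.25. What happens inside it depends on the unstated combination rule:

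- If either sign suffices, as the wording of Annexe 3a suggests, the label changes when DTF is in the band and excursion is at least 2.5 cm.
- If both signs are required, it changes when DTF is in the band and excursion is below 2.5 cm.

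The conflict survives under both readings.

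**4. Example (assumed values, either-sign reading).** Te = 2.0 mm, Ti = 2.45 mm, excursion 3.0 cm. DTF = (2.45 − 2.0) / 2.0 × 100 = 22.5%. This is no dysfunction under section 6.5.2.3 and dysfunction under Annexe 3a.

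**5. Width of the band.** It is (1.25 − 1.20) × Te = 0.05 × Te. The values of Te are assumptions.

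| Te (mm) | Ti at 20% (mm) | Ti at 25% (mm) | Width (mm) |
|---|---|---|---|
| 1.5 | 1.80 | 1.875 | 0.075 |
| 2.0 | 2.40 | 2.50 | 0.10 |
| 3.0 | 3.60 | 3.75 | 0.15 |

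This describes the band, not how often scans fall in it.

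**6. How many patients?** The documents give no basis for an estimate. If 2%, 5% or 10% of the planned 150 patients (section 8.1) had a reading in the band, that would be 150 × 0.02 = 3, 150 × 0.05 = 7.5 or 150 × 0.10 = 15 patients. These shares are assumptions. They are also upper limits on the number of changed labels, because the excursion condition in step 3 must hold as well.

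**7. Can the label be rebuilt from recorded thickness?** Annexe 4 records thickness in cm and states no precision. If it is rounded to 0.01 cm (assumption), recorded values of 0.20 and 0.24 cm give 20.0%. The true DTF could then lie from (0.235 − 0.205) / 0.205 = 14.6% to (0.245 − 0.195) / 0.195 = 25.6%, a range that spans both cut-offs.

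**The case against.** The strongest reply is that the main text can be read as governing. It calls its list definitional and attaches a reference to its figure, whereas the annexe is cited for technique and gives its figure without a reference. That reading is reasonable, but nothing in the plan makes it the rule, and the annexe states its cut-off without qualification.

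The second reply is that the consequence is narrow. On the either-sign reading, any side with excursion below 2.5 cm gets the same label under both texts. The clinical physiotherapist also sees the measured values, is trained to interpret the reports, and sets treatment for the primary hypothesis only. The label can therefore sway the compatibility judgement without fixing it. The study has one group, so no comparison between arms can be biased. All of this stands. It limits the weight of the point and places the clearest exposure in the secondary analyses of sections 8.2.2 and 8.2.3. It does not remove the contradiction, and the documents contain nothing to show that the effect is negligible.

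The validation step in French centres limits uncontrolled labelling there. It is stated only for French operators, and it does not tell the checker which cut-off to use.

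**Conclusion.** The contradiction holds: sections that operators are expected to use give different cut-offs for the same sign, with no stated precedence. It should be corrected, although there is no evidence that it would overturn the primary result.

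The most direct exposure is 2 of the 11 clinical hypotheses in section 6.5.1.4 and 1 of the 8 kappa categories in section 8.2.3. These are counts of list entries, not of patients. The number of patients is unknown, and the thicknesses, rounding and band shares used above are assumptions. The text conflict itself rests on no assumption. Which scans it affects depends on how excursion and thickening fraction combine, and the plan leaves that open too.

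The effect on kappa has a further condition: it arises only where diaphragm dysfunction is the ultrasound diagnosis entered in the table. Section 7.4.4 and Annexe 4 allow several diagnoses per scan, while the table takes one, and the plan does not say how several are reduced to one. That is a separate gap.

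**What to change.** **Before inclusion.** Reconcile section 6.5.2.3 and Annexe 3a to one thickening-fraction cut-off, and state how it combines with excursion on each side. Both choices belong to the sponsor's clinical experts; this review takes no view on either. Printing the agreed cut-off and rule on the Annexe 4 form is a useful addition, because that is where the label is assigned.

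**If scans have already been reported under mixed cut-offs.** Use the recorded thickening fraction and excursion for a sensitivity check of the ultrasound diaphragm label in the kappa analysis only. First state which recorded ultrasound diagnosis enters the table when there are several. The recorded percentage is preferable to recalculation from rounded thickness, provided it was calculated from unrounded measurements; otherwise it carries the same rounding error. Compatibility judgements and treatment decisions already made from issued reports cannot be re-derived and should stay as recorded.

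**Cost.** A correction in two places and one printed line. No new measurement is needed, since Annexe 4 already collects thickness, thickening fraction and excursion for each side.

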6.5.2.4. Lung and diaphragm ultrasound report

The physiotherapist/operator will write a detailed LUS-scan report, which will be given to the clinical physiotherapist. When LUS is performed by a french physiotherapist, the LUS report will be checked and validated by the referent intensiviste.-The LUS-scan report# will include the LUS and Diaphragm diagnosis and describe the signs observed in the different regions of the chest (*cf. annexe4*). The clinical physiotherapist is trained to interpret LUS reports. The clinical physiotherapist then determines the options or changes to treatment based on the US findings.

7. Studyprogress

7.1.Study planning

- Ethic comittee submission: December 2016;
- Study comencement: January 2016;
- Inclusion duration : 12 months;
- Length of patient participation: one day;
- End of inclusion: January 2017;
- Total duration of the study: 18 months;
- Congress communications: French Intensive Care Society Congress, ESICM, ERS, ATS, from April 2018;
- Publication: September 2018;
- Target journal: Physical therapy, Intensive Care Medicine or Critical Care Medicine.

7.2.Recruitment method

Patients will be recruited in the Surgical ICU of the CHU de Dijon, Medical-Surgical ICU of Paris St. Joseph's Hospital, Respiratory ICU and Post-ICU Rehabilitation Unit of Forcilles' Hopital and the ICU of St Vincent's Hospital.

Patients admitted to the ICU and who meet the inclusion criteria will be invited to take part in the study. Patients with hypoxemia will be identified by the duty physician at the time of

transfer to the unit or by the principal investigator and the coordinating investigator during the day. Written informed consent will be collected (*cf. annexes 5a and 5b*).

7.3. Number of patients to recruit and duration of participation for each patient

Given the high prevalence of hypoxemia in ICUs, the systematic respiratory assessment in these patients by the physiotherapist and our relatively non-restrictive inclusion criteria, we believe we can recruit more than 300 patients per year.

7.4. Data collected

7.4.1. Pre-inclusion visit

The pre-inclusion visit takes place as soon as a patient meeting the inclusion criteria is hospitalized in the ICU department. During this visit, the principal investigator will give the patient or his relatives the information consent (*cfannexe5*). If the patient gives his/her consent, he/she will be included in the study.

